5.2.8. Secondary Efficacy Outcome and Methodology

The continuous secondary efficacy outcomes include:

- Actual and change in HbA_{1c} from baseline to 4, 8, 12, 16, and 20 weeks or LOCF
- 7-point SMBG measurements as listed in the Study Schedule (see ABET Study Protocol Attachment 1)
 - premeal for each meal

- postmeal for each meal
- bedtime
- summaries of 7-point SMBG (actual and change from baseline)
 - daily mean BG level (average across all 7 time points)
 - daily mean premeal BG level (before breakfast, lunch, dinner)
 - daily mean postprandial BG level (breakfast, lunch and bedtime)
- inpatient variability, as measured by the SD of the 7-point SMBG
- actual and change from baseline in weight and BMI
- actual and change from baseline in basal insulin doses (U/day and U/kg/day)
- patient-reported outcomes as reflected in responses to ITSQ

The analysis of the change from baseline of continuous secondary efficacy variables will be performed using the same MMRM model for the primary efficacy analysis with treatment (LY2963016, Lantus®), entry use of insulin secretagogue (SU, meglitinide, neither), visit, and interaction between visit and treatment as fixed effects; the baseline value of the response variable and the baseline HbA_{1c} value as covariates; and a random effect for patient.

The proportion of patients achieving HbA_{1c} target values (HbA_{1c} level <7.0% and ≤6.5%) at any point during the study (Weeks 4, 8, 12, 16, 20, and 24 and 24-week endpoint [LOCF]) will be analyzed using Fisher's exact test or Pearson's chi-square test.

A plot of the actual and change from baseline in weight (kg) will be presented.

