**Reference Therapy, Dose, and Mode of Administration or Comparative Intervention:**

Patients will initiate treatment with a starting dose of 10 U of Lantus® QD and will then be supervised by investigators through the course of the study to maintain the FBG  $\leq$ 100 mg/dL (5.6 mmol/L) while avoiding hypoglycemia. The mode of administration will be subcutaneous.

**Criteria for Evaluation:**Efficacy

Primary Endpoint:

Change in HbA1c from baseline to 24 weeks.

Secondary Endpoints:

- Change in HbA1c from baseline to 4, 8, 12, 16, and 20 weeks or last post-baseline observation carried forward (LOCF)
- Percentage of patients with HbA1c <7%; percentage of patients with HbA1c  $\leq$ 6.5%
- 7-point SMBG (expressed as plasma-equivalent glucose values obtained before each meal; after each meal; at bedtime)
- Inpatient variability as measured by the standard deviation (SD) of the 7-point SMBG
- Basal insulin dose in total units per day and daily units per kilogram
- Weight change
- Patient-reported outcomes as reflected in responses to ITSQ

Safety:

Anti-glargine antibodies, laboratory measurements, adverse events (AEs), serious adverse events (SAEs), and hypoglycemia will be evaluated for safety. Episodes of severe hypoglycemia will be captured as SAEs. Certain outcomes, such as death, early discontinuation because of AE, and investigator decision to discontinue a subject will also be evaluated for safety. Patients will report hypoglycemia, which is defined as an event associated with signs or symptoms consistent with hypoglycemia or a blood level of  $\leq$ 70 mg/dL ( $\leq$ 3.9 mmol/L), even if it is not associated with signs or symptoms.

Injection-site reactions and neoplasms will be captured as AEs.

Health Outcomes:

Patient-reported outcomes as reflected in responses to ITSQ. The ITSQ is a validated instrument containing 22 items that assesses treatment satisfaction for persons with diabetes who are taking insulin.

**Statistical Methods:**Sample Size:

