#### **7.2.3. Blood Glucose Monitoring Plan**

Patients will be provided with glucometers and corresponding glucose test strips so they can obtain SMBG values. Blood glucose values will be utilized to guide insulin titration dosing; to determine hypoglycemia, as specified in the protocol; and to ensure that uniform data are collected. Glucose test strips will be distributed according to national regulations.

Throughout the study, patients will be instructed to check their FBG values daily to assess the need for dose adjustments. The first recorded BG value for each profile should be a premorning meal BG value followed by the other specified BG values through the day for consistency.

- In the week prior to telephone visits, patients will be instructed to complete 4-point SMBG values (once before each meal and at bedtime) recorded on 3 separate days (preferably most recent readings). Four-point SMBG values reported during telephone visits will be recorded at the subsequent office visit and Visit 801.
- Patients will be instructed to complete 7-point SMBG profiles on 2 separate days in the 2-week period prior to Visits 2, 4, 8, 12, and 18 (preferably most recent readings). The SMBG profiles will consist of:
  - before the morning meal, midday meal, and evening meal; 2-hour postprandial measurements for the morning, midday meal, and evening meal; at bedtime.
  - In case of unexplained morning hyperglycemia, investigators shall instruct patients to conduct additional 3am and prebreakfast BG to identify the cause.

Missing values in SMBG profiles that do not reflect noncompliance with the protocol, in the opinion of the investigator, will not be considered a protocol deviation.

Patients may be requested by investigators to perform more intensive self-monitoring, if clinically indicated. Patients should record all BG values in their study diaries.

The morning premeal measurement should be done fasting before breakfast. Data from the 7-point SMBG profiles measured prior to Visits 2, 4, 8, 12, and 18 will be used to assess the effect of the treatments on daily BG values and should, therefore, be transferred to the eCRF at those visits. In the case of ED, 7-point SMBG values from the patient's study diary after the previous office visit should be entered into the eCRF, as are available. Patients should record all BG values (and insulin doses after Visit 2) in their study diaries.

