### **12.2.7. Secondary Efficacy Outcome and Methodology**

The continuous secondary efficacy outcomes include:

- change in HbA1c from baseline to 4, 8, 12, 16, and 20 weeks or LOCF
- 7-point SMBG measurements as listed in the Study Schedule ([Attachment 1](#))
  - premeal for each meal
  - postmeal for each meal
  - bedtime
- inpatient variability, as measured by the SD of the 7-point SMBG
- basal insulin dose (24-hour total measured in U/d and U/kg) at end of study
- weight change

The analysis of the continuous secondary efficacy variables will be performed using the same MMRM model for the primary efficacy analysis with the baseline value of the response variable added as a covariate with the FAS population. The proportion of patients achieving HbA1c target values (HbA1c level  $<7.0\%$  and  $\leq 6.5\%$ ) at any point during the study (Weeks 4, 8, 12, 16, 20, and 24 and 24-week endpoint [LOCF]) will be analyzed using Fisher's exact test or Pearson's chi-square test.

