# Patients who discontinue early from the study will complete Visit 801.

- a For visit window purposes, the visit will end on the last day the patient completes a study procedure or assessment. Visits should occur within the visit intervals indicated. The timing of visits (including allowable deviations) should be based on time postrandomisation.
- b Additional training should be provided as needed throughout the study.
- c Adverse events, hypoglycemic episodes, concomitant medications and the last 3 available profiles of 4-point SMBG reported at telephone visits should be recorded on the eCRF at the next office visit. The 4 points are: before morning, mid-day, and evening meals, and at bedtime.
- d The measurements should be done fasting before breakfast.
- e Patients should perform two 7-point SMBG profiles during the 2-week period prior to these visits (preferably most recent readings). The 7-points are before the morning, midday, and evening meals; 2 hours after the morning, midday meal, and evening meal; at bedtime.
- f Transfer values from the study diary if available.
- g Dispense glucose meter supplies as needed; may not be at every visit.
- h Study sites will retain study diaries.
- i The 3 days of 4-point SMBG values used as a reference from the telephone visit need to be validated and entered into the eCRF from the source diaries. These values should be within 1 week (or 2 weeks, if applicable) prior to the telephone visit preceding the office visit when data are transferred to eCRF. In certain instances (for example, between Visits 2 and 4), it may be from the same days as those used for the 7-point SMBGs.
- j Analyses should be performed at a central laboratory unless otherwise noted and can be repeated for cause in case of adverse events.
- k Serum pregnancy test will be performed on all females of childbearing potential at Visit 1 and when clinically indicated, and will be analyzed by a central laboratory. Urine pregnancy tests at other visits can be accepted per local regulations. A urine pregnancy test may be repeated locally for any visits if considered necessary by the investigators and/or in compliance with local regulations.
- l Blood samples for immunogenicity testing will be collected to determine antibody production against LY2963016 or Lantus®.
- m Study sites will retain questionnaires.
- n This questionnaire should be administered only if the patient has received at least 1 dose of study drug.

---

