Values for the 7-point self-monitored blood glucose (SMBG) blood glucose profiles will be averaged over the two 7-point SMBG profiles obtained during 2-week period prior to each office visit (as specified in Protocol Section 7.2.3). For the average blood glucose calculation for a specific time point, if only 1 of 2 days of data is collected, then the value of the 1 day will be used. If 2 days of data are collected, then the average of the 2 days will be used. If more than 2

days of data are collected then choose the 2 according to the ranking first by the number of non-missing blood glucose measurements and then by day closest to the visit day. The handling of missing data for the ITSQ questionnaire is specified in Section 5.2.10.

Visits for laboratory data will be handled by conventions in the Lilly diabetes white paper (Standardization of Derivations for Efficacy Lab Variables).

All analyses will be implemented using SAS Version 9.4® or higher.

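### The SAP's daily mean postprandial glucose uses the bedtime reading in place of the reading after the evening meal

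*SAP*

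**What the plan says.** SAP Section 5.2.8 lists three summaries of the 7-point self-monitored glucose profile, as actual values and as change from baseline, among the continuous secondary efficacy outcomes:

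- the overall mean, "daily mean BG level (average across all 7 time points";
- the premeal mean, "daily mean premeal BG level (before breakfast, lunch, dinner";
- the postprandial mean, "daily mean postprandial BG level (breakfast, lunch and bedtime".

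The protocol defines the seven readings in Section 7.2.3. After the three premeal readings it lists "2-hour postprandial measurements for the morning, midday meal, and evening meal; at bedtime". Footnote e to the Study Schedule (Attachment 1) gives the same set: "2 hours after the morning, midday meal, and evening meal; at bedtime". The synopsis makes the same split, with values "obtained before each meal; after each meal; at bedtime". SAP Section 5.2.8 itself lists the post-meal readings and bedtime as separate individual outcomes just above the summaries.

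**The concern.** The name says postprandial, but the component list mixes two post-meal readings with one that neither document calls postprandial. The protocol collects both an evening post-meal value and a bedtime value, so it does not treat them as interchangeable. The post-meal readings have a fixed 2-hour interval; bedtime has no stated interval after any meal.

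If the rule is programmed as written, a listed secondary outcome analysed by MMRM would be reported as postprandial glucose while one third of it is bedtime glucose. A reader would reasonably assume that all three meals are covered. If a programmer quietly uses the evening post-meal value instead, the output departs from the approved SAP with no record of the change. Either way the definition needs a written correction.

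**Working it through.** The plan states no figure to reproduce here. The check compares the component lists and then derives the size of the discrepancy.

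**Components**

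| Source | Component 1 | Component 2 | Component 3 |
|---|---|---|---|
| Protocol 7.2.3 and Attachment 1, footnote e: post-meal readings | after morning meal | after midday meal | after evening meal |
| SAP 5.2.8: postprandial mean | breakfast | lunch | bedtime |
| SAP 5.2.8: premeal mean | breakfast | lunch | dinner |

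One of three components differs (1/3 = 33.3%): the evening post-meal reading is missing and bedtime is added.

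**Does other text settle it?** SAP Section 5.2.1 covers only how repeat profiles are combined, for example "If 2 days of data are collected, then the average of the 2 days will be used", and takes those profiles from Protocol 7.2.3, the section that keeps the two readings apart. The SAP revision history does not mention the point. Protocol Section 12.2.7 lists "7-point SMBG measurements as listed in the Study Schedule" and the SD of the profile, but no postprandial mean, so there is no protocol definition of this summary to fall back on.

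**Size.** Let B, L and D be the values after the morning, midday and evening meals, and T the bedtime value. With equal weights and all readings present:

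SAP value − three-meal mean = (B + L + T)/3 − (B + L + D)/3 = (T − D)/3.

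The documents contain no glucose data, so every gap below is an assumption.

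| Quantity reported | Assumed input (mg/dL) | Shift = input/3 (mg/dL) |
|---|---|---|
| Level at a visit | absolute gap between T and D: 0, 10, 20, 40 | 0, 3.3, 6.7, 13.3 |
| Change from baseline | change in that gap since baseline: 0, 5, 10, 20 | 0, 1.7, 3.3, 6.7 |
| Treatment contrast | between-arm difference in that change: 0, 3, 6, 15 | 0, 1, 2, 5 |

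A gap that stays constant over time cancels from the change from baseline. A gap that changes equally in both arms cancels from the treatment contrast. The last two rows are for unadjusted means; the MMRM also adjusts for the baseline of the response, which would itself be built with bedtime.

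**Missing readings.** The SAP gives no rule for a missing time point within this mean. If available readings were simply averaged and one post-meal value were missing, bedtime would carry 1/2 of the weight instead of 1/3.

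**The case against.** The strongest case is that this is a labelling slip with almost no consequence. The summary was added by the SAP and does not appear in the protocol's secondary list, so no protocol endpoint is contradicted. The formula is disclosed in parentheses. No noninferiority or equivalence decision uses it. Both arms share one definition and one titration algorithm, so there is no clear bias toward either product. Each post-meal reading is still analysed by visit, and a reader could average those results to approximate the three-meal mean. The secondary objective concerns the 7-point profile, which the individual time points address without this summary. The numerical ranges rest on assumed gaps.

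Most of this stands, and it limits the weight of the point. It does not remove it. The line is a stated derivation rule for a listed secondary outcome, and a programmer would follow it. Disclosing the components in the SAP does not help someone reading a results table headed postprandial. The neighbouring premeal line, with breakfast, lunch and dinner, makes a slip likely, but the documents do not confirm it. Only the identity (T − D)/3 is established; the numbers built on it illustrate scale and are not estimates.

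**Conclusion.** The definition is wrong as written: one third of the SAP's postprandial mean is not a postprandial value under the protocol. That share assumes equal weights and complete readings. The error in the reported level is exactly one third of the bedtime-to-evening-post-meal gap, whose size and sign the documents do not give. The main damage is to the reported levels and to what the label means; the effect on the between-arm contrast may be zero.

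The evening post-meal reading is not lost. It remains in its own time-point analysis, in the 7-point mean and in the 7-point SD. The primary analysis, the gated reverse comparison, the sample size and the safety analyses do not depend on this variable. It should be corrected because the error is plain and the remedy is nearly free, but it does not threaten the trial's main conclusions.

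**What to change.** Before database lock, redefine the summary in SAP Section 5.2.8 as the mean of the three 2-hour post-meal readings (morning, midday and evening meals). Keep bedtime as its own time point and within the 7-point mean and SD, as already planned. If bedtime was meant, rename the summary so that it no longer claims to be postprandial, and state why that combination was chosen.

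The cost is one word in the SAP and one derived variable. The evening post-meal reading is already collected for Visits 2, 4, 8, 12 and 18, so no new data are needed. SAP Version 2 is due for approval before the lock, so the correction can be made at that step.

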## 7. Investigational Plan

### 7.1. Summary of Study Design

Study I4L-GH-ABET (ABET) is a Phase 3, prospective, randomized, multicenter, 2-arm, active control, open-label, parallel-design, 24-week study with a 4-week post-treatment follow-up. The study will compare 2 long-acting basal insulin analogs (LY2963016 and Lantus®) in patients with T2DM who are insulin naïve and have failed to achieve adequate glycemic control on at least 2 OAMs. This study is designed to determine noninferiority of LY2963016 to Lantus® in change in HbA1c from baseline when used to initiate insulin therapy in this patient population.

[figure not shown]
A total of 530 patients are planned to be enrolled in the study, with a target to complete 450 patients. Patients will be screened at Visit 1, and eligible patients will be randomized at Visit 2 to receive LY2963016 or Lantus® QD with at least 2 OAMs for a period of 24 weeks at which the efficacy endpoint of change in HbA1c levels from baseline will be assessed.

Patients will be contacted over the telephone in-between office visits (described as “Telephone Visits” in Section 7.2.2.3.1) to be queried about the entry in their diaries regarding any AEs, hypoglycemia, insulin self-administration, etc.

At approximately 4-week post-treatment endpoint (Visit 801), patients will have a final clinic visit at which information will be collected according to the Study Schedule ([Attachment 1](#)). The starting dose is 10 units (U), which will be titrated by the weekly dosing algorithm as described in Section 9.5 until fasting blood glucose (FBG) reaches  $\leq 100$  mg/dL (5.6 mmol/L) (weekly-base titration till Visit 10 and titration as needed afterwards. The insulin doses can be adjusted between intervals at discretion of the investigators. The titration procedure during the study will occur as described in Section 9.5.

End of study (trial) is the date of the last visit or last scheduled procedure shown in the Study Schedule for the last active patient in the study.

[Figure ABET.7.1](#) illustrates the study design.

Abbreviations: OAM = oral antihyperglycemic medication; QD = once daily;  
\* = telephone visit.

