Unless otherwise noted, all tests of treatment effects will be conducted at a 2-sided alpha level of 0.05, and confidence intervals (CIs) will be calculated as 2-sided 95% CIs. All tests of interactions between treatment groups and other factors will be conducted at a 2-sided alpha level of 0.05. No adjustments for multiplicity will be performed. See Section 5.2.7 for the gate-keeping strategies used for primary/secondary endpoints.

The baseline is Visit 2. If baseline data are missing, the last measurement taken prior to this visit will be used for the baseline measurement.

The last visit for the 24-week treatment study is Visit 18. If the Visit 18 measurement is missing, the last post-baseline value will be carried forward to create the 24-week endpoint value using the last-observation-carried-forward (LOCF) methodology. If there are no measurements after Visit 2 (date of randomization), the 24-week endpoint values will be considered missing. Efficacy analyses only be conducted for patients with both nonmissing baseline value and at least 1 nonmissing post-baseline value.

The LOCF methodology will be utilized in the endpoint analyses using analysis of covariance (ANCOVA) of HbA_{1c}, laboratory chemistry and hematology, as well as analysis of hypoglycemia (rate and incidence) and insulin antibodies.

Unless otherwise noted, the analysis of the continuous secondary efficacy and safety measurements (SMBG at each time point and summaries of SMBG, weight, dose, and vital signs) will use the same mixed model repeated measure (MMRM) methodology for the primary efficacy analyses with the baseline value of the response variable as a covariate with the FAS patient population. Continuous laboratory measures will be analyzed using an analysis of covariance (ANCOVA) model.

For categorical measures, Fisher's exact test will be used. To avoid computational problems, a maximum computation time of five minutes will be programmed into the analysis for Fisher's exact test. If it does not converge in that time, the Pearson's Chi-square test will be utilized.

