1. The relationship between the natural logarithm of the last observed insulin antibody levels ($\text{Ln}[\text{antibody level}]$) and selected clinical response variables (efficacy and safety measures (eg HbA_{1c}, total hypoglycemia rate, basal dose [U/day, U/kg/day],) will be evaluated using scatterplots and analyzed using ANCOVA on efficacy/safety

measure as the dependent variable with treatment, and entry use of insulin scretagogue (SU, meglitinide, neither) as fixed effects; baseline HbA_{1c} value, baseline response variable, Ln(antibody level) and treatment-by-Ln(antibody level) interaction as covariates for the FAS patients with detectable antibodies postbaseline and with valid antibody testing at baseline (detected, ND). A significant treatment-by-insulin antibody interaction may be indicative of a differential treatment effect necessitating further exploration to determine the nature of the interaction. Only patients with non-missing baseline value and at least one non-missing post-baseline value of the clinical response variable will be included in the analysis.

2. The relationship between TEAR and selected clinical response variables (efficacy and safety measures (e.g. HbA_{1c}, total hypoglycemia rate, basal dose [U/day, U/kg/day],) will be analyzed using ANCOVA on efficacy/safety measure as the dependent variable with treatment, TEAR (yes/no), entry use of insulin scretagogue (SU, meglitinide, neither), treatment-by-TEAR interaction as fixed effects, baseline response variable and baseline HbA_{1c} value as a covariate for the FAS patients with detectable antibodies postbaseline and with valid antibody testing at baseline (detected, ND). A significant treatment-by-TEAR interaction may be indicative of a differential treatment effect necessitating further exploration to determine the nature of the interaction. Only patients with non-missing baseline value and at least one non-missing post-baseline value of the clinical response variable will be included in the analysis.

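### Basal insulin dose is put under a change-from-baseline model with baseline dose as covariate, but insulin-naive patients have no recorded baseline dose and none is defined

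*SAP*

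**What the plan says.** Basal insulin dose is one of the measures compared under the secondary objectives (Protocol 6.2, SAP 4.2). SAP 5.2.8 lists the outcome as "actual and change from baseline in basal insulin doses (U/day and U/kg/day"). The model given there is for change from baseline and includes "the baseline value of the response variable and the baseline HbA_{1c} value as covariates". SAP 5.2.1 names dose, with SMBG, weight and vital signs, among the variables that get this type of model. It sets baseline at Visit 2, or the last measurement before it, and adds: "Efficacy analyses only be conducted for patients with both nonmissing baseline value and at least 1 nonmissing post-baseline value".

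Protocol 7.1 describes patients "who are insulin naïve and have failed to achieve adequate glycemic control on at least 2 OAMs". On recording, Protocol 7.2.3 says: "Patients should record all BG values (and insulin doses after Visit 2) in their study diaries". In the Study Schedule (Attachment 1), the row for insulin dose on the day before the visit is blank at Visits 1 and 2 and starts at Visit 3. Every patient starts at 10 U, first injected at Visit 2 (Protocol 7.2.2.2.1.1 and 9.5).

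Protocol 12.2.7 lists dose as a level rather than a change, but also carries the baseline-of-response covariate. SAP 5.2.11.4 repeats the term in its antibody ANCOVAs, which name basal dose as a response. Item 1 has "baseline response variable, Ln(antibody level) and treatment-by-Ln(antibody level) interaction as covariates".

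**The concern.** The general rule suits weight or blood pressure, which have a pre-treatment value. Basal dose has none in this population. The analysis therefore cannot be run as written until someone supplies a baseline, and the SAP does not say which.

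Dose matters here because both arms are titrated to the same fasting glucose target. Similar HbA1c is easier to interpret if it was reached with similar amounts of insulin. A comparison that serves this purpose should not rest on a definition settled during programming, least of all in an open-label trial. The SAP's Revision History places approval of version 2 before unblinding and database lock, which is the point at which to settle it.

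**Working it through.** The plan gives no figure for the dose analysis. Its only related figure, the sample size for the primary test, reproduces. With 300 and 150 completers and an SD of 1.3, the SE is 1.3 × sqrt(1/300 + 1/150) = 0.130. Power is Φ(0.40/0.130 − 1.96) = Φ(1.117) = 0.868, which is over 85%. With 15% dropout, 450/0.85 = 529.4, so 530 are randomized. Nothing below changes this.

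**Is there a recorded baseline dose?** The baseline rule needs a value at Visit 2 or earlier. The schedule has no dose entry at Visits 1 or 2, and diaries hold doses only after Visit 2. Attachment 1 does list previous insulin exposure at Visit 1, but Protocol 7.2.2.1 treats this as medical history, not as a dose measurement. The documents therefore provide no recorded value.

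**What each reading does.** Write y for post-baseline dose and b for baseline dose. The model fits y − b on treatment, the other terms and b.

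- *b missing for all.* The nonmissing-baseline rule keeps 0 of 530 patients.
- *b = 0 U for all.* Change equals actual dose. The covariate is a column of zeros and drops out.
- *b = 10 U for all, U/day.* The covariate is constant and aliased with the intercept. Each arm's mean change is 10 U/day below its mean actual dose, and the arm difference is the same.
- *b = 10 U for all, U/kg/day.* The covariate is 10/weight, for example 10/50 = 0.200 at 50 kg and 10/90 = 0.111 at 90 kg. It varies between patients, so the model adjusts for inverse body weight.

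**Illustration.** A single-visit linear model was fitted to one simulated data set of 530 patients (353 and 177). Assumed values: weight with mean 68 kg and SD 11 kg, baseline HbA1c with mean 8.5% and SD 1%, skewed doses that increase with weight, and no true arm difference.

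| Response | Baseline dose | Patients kept | Design rank | Arm difference (SE) |
|---|---|---|---|---|
| U/day | missing | 0 | – | – |
| U/day | 0 U | 530 | 5 of 6 | −0.863 (0.809) |
| U/day | 10 U | 530 | 5 of 6 | −0.863 (0.809) |
| U/day | none in model | 530 | 5 of 5 | −0.863 (0.809) |
| U/kg/day | missing | 0 | – | – |
| U/kg/day | 0 | 530 | 5 of 6 | −0.0033 (0.0121) |
| U/kg/day | 10/weight | 530 | 6 of 6 | −0.0086 (0.0119) |
| U/kg/day | none in model | 530 | 5 of 5 | −0.0033 (0.0121) |

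The U/kg/day estimate moves by 0.0086 − 0.0033 = 0.0053, or 0.0053/0.0121 = 0.44 of a standard error. The size of that shift belongs to the simulated data. That there is a shift follows from the covariate not being constant.

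**Possible gain from baseline weight in the U/day model.** A covariate with correlation r to the outcome lowers the SE of the arm difference by about 1 − sqrt(1 − r²). This is 1 − sqrt(0.91) = 4.6% at r = 0.3 and 1 − sqrt(0.75) = 13.4% at r = 0.5. The documents give no weight–dose correlation, so 0.3 to 0.5 is an assumption.

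**The case against.** The strongest reply is that the baseline is known even though it is not recorded: 0 U before Visit 2 by design, and 10 U at Visit 2 by protocol. A competent programmer would not set it to missing. Under either constant the U/day arm difference and SE are exactly those of a model without the covariate. Adjusting U/kg/day for inverse baseline weight uses a pre-randomization variable and is legitimate. SAP 5.2.8 also lists actual dose, and the outcome is outside the gated tests.

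Most of this stands, and it limits the point. It does not remove it. The SAP never says which value applies, the U/kg/day result depends on the answer, and the modelling sentence in 5.2.8 covers change only. The SAP also shows that an exception was feasible: the treatment satisfaction questionnaire, likewise not administered before treatment, has its own model with baseline HbA1c as the only covariate (SAP 5.2.10.1).

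A reader might infer three stronger things that the documents do not support.

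- *That the dose objective cannot be analysed at all.* This holds only on the literal missing-baseline reading. A constant baseline gives a usable U/day comparison.
- *That the first recorded dose would serve as baseline and is already affected by titration.* Neither document proposes this. The Visit 3 record is the dose on the day before that visit, and scheduled titration starts at Visit 3 (Protocol 9.5), so only discretionary earlier changes could affect it.
- *That Protocol 12.2.7, with "basal insulin dose (24-hour total measured in U/d and U/kg) at end of study", brings in post-treatment doses from Visit 801.* The protocol defines end of study as a date for the whole trial, not a patient-level time point, and SAP 5.2.1 makes Visit 18 the last visit of the treatment study.

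**Conclusion.** The point holds as a specification fault in one ungated secondary outcome. As written, the dose analysis requires a baseline that no patient has on record, so the literal analysis set is 0 of 530. With a constant baseline the U/day comparison is unaffected and its covariate is merely redundant. The U/kg/day comparison depends on whether the unstated baseline is 0 U or 10 U. In the basal-dose ANCOVAs of SAP 5.2.11.4 the same term and the same nonmissing-baseline condition apply, with the same consequences.

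The algebra needs no assumed data. The simulated estimates are illustrations only, and the 5% to 13% SE gain from baseline weight depends on the assumed correlation. The primary and key secondary HbA1c tests and the sample size are untouched. The change should be made before database lock, but it does not threaten the trial's main conclusion.

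**What to change.** - In SAP 5.2.1 and 5.2.8, exempt basal insulin dose from the change-from-baseline, baseline-covariate and nonmissing-baseline rules.
- Analyse actual dose, in U/day and U/kg/day, at post-baseline treatment visits through Visit 18. Use an MMRM with treatment, visit, treatment-by-visit, entry secretagogue use and baseline HbA1c. Add baseline body weight for U/day. Report the Week 24 arm difference with its 95% CI.
- In SAP 5.2.11.4, items 1 and 2, drop the baseline response term, and the nonmissing-baseline condition tied to it, when the response is basal dose.

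The cost is SAP wording. Doses are already collected from Visit 3 and weight is already measured at Visit 2, so no new data are needed. Protocol 12.2.7 carries the same covariate, but Protocol 12.2.1 and SAP 5.2.1 let a change that is not to a principal feature be described and justified in the SAP without an amendment.
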